## 6 Treatment

### 6.1 Study treatment

The investigational drugs to be used in this study are capmatinib and spartalizumab, as described in [Table 6-1](#). The study treatment is defined as capmatinib plus spartalizumab or capmatinib plus placebo.

#### 6.1.1 Investigational drugs

The treatment period begins on Cycle 1 Day 1. In other words, the first dose of study treatment (capmatinib plus spartalizumab or capmatinib plus placebo) is given on Day 1 of Cycle 1. The duration of each treatment cycle is 28 days.

Refer to [Section 6.7.2](#) for study drug prescribing and administration information.

Spartalizumab will be supplied as concentrate for solution in open label vials and it will be diluted in dextrose 5% in water (D5W). Spartalizumab matching placebo will be D5W for infusion supplied by the site.

**Table 6-1 Investigational drugs**

Investigational Drugs	Pharmaceutical Dosage Form	Route of Administration	Drug package	Supplier (global or local)	Dose and Regimen
Name and Strengths					
Capmatinib (INC280) 150 mg or 200 mg	Film-coated tablet	Oral use	Open label, patient specific bottles	Global	400 mg BID
Spartalizumab (PDR001) 100 mg	Concentrate for solution for infusion	Intravenous use	Open label, patient specific vials	Global	400 mg Q4W

#### 6.1.2 Additional study treatments

No other treatment beyond the investigational drugs described in [Section 6.1.1](#) are included in this trial.

#### 6.1.3 Treatment arms

Following the study enrollment halt, spartalizumab treatment has been discontinued and Part 2 will not be initiated.

#### Part 1: Single Arm Run-in Part

All eligible subjects enrolled in Part 1 will be treated with capmatinib 400 mg orally twice daily (BID) in combination with spartalizumab 400 mg iv every 28 days (Q4W).

A complete cycle of treatment is defined as 28 days of continuous capmatinib treatment and an infusion of spartalizumab every 28 days.

## Part 2: Randomized Part

All eligible subjects enrolled in Part 2 will be assigned to one of the following treatment arms in a ratio of 2:1 according to stratification factors.

- Arm 1: capmatinib 400 mg orally twice daily (BID) plus spartalizumab 400 mg intravenously (iv) every 28 days (Q4W).
- Arm 2: capmatinib 400 mg orally twice daily (BID) plus spartalizumab matching placebo iv every 28 days (Q4W).

A complete cycle of treatment is defined as 28 days of continuous capmatinib treatment and an infusion of spartalizumab or placebo every 28 days.

### 6.1.4 Treatment duration

Subjects will be treated until they experience unacceptable toxicity, disease progression per RECIST 1.1 as determined by investigator assessment (with or without confirmation by BIRC), and/or treatment is discontinued at the discretion of the investigator or the subject. A complete list of the circumstances requiring study treatment discontinuation is provided in [Section 9.1.1](#).

Subjects may continue treatment beyond disease progression if, in the judgment of the investigator, there is evidence of clinical benefit and the patient wishes to continue on the study treatment. Criteria for treatment beyond progression are described below.

### Treatment beyond disease progression

Subjects will be permitted to continue study treatment beyond disease progression per RECIST 1.1 as determined by investigator, provided they meet all the following criteria:

- Clinical benefit per investigator's judgement
- Continuation of treatment beyond initial progression will not delay an imminent intervention to prevent serious complications of disease progression
- Subject exhibits adequate tolerance to study treatment
- Subject performance status is stable
- Absence of symptoms and signs (including worsening of clinically relevant laboratory values) indicating disease progression

The reasons for the subject continuing treatment beyond progression will be documented in the eCRF.

[figure not shown]
Subjects who meet the above criteria and continue study treatment beyond initial disease progression per RECIST 1.1 will continue all study procedures as outlined in [Table 8-1b](#) and [Table 8-3](#).

In addition, subjects enrolled in Part 2, who continue study treatment beyond initial disease progression per RECIST 1.1 [REDACTED]. In case of clinical deterioration or suspicion of disease progression, a follow-up imaging assessment should be performed promptly rather than waiting for the next scheduled assessment.

[REDACTED]

[REDACTED]

[REDACTED]

Please refer to [Section 8.3](#) for additional information on RECIST 1.1 [REDACTED].

## 6.2 Other treatment(s)

If a subject experiences an infusion reaction, he/she may receive pre-medication on subsequent dosing days. The pre-medication should be chosen per institutional practice at the discretion of the treating physician.

Acute allergic reactions should be treated as needed per institutional practice or the dose modification guideline ([Section 6.5.1](#)). In the event of anaphylactic/anaphylactoid reactions, this includes any therapy necessary to restore normal cardiopulmonary status. If a subject experiences a Grade  $\geq 3$  anaphylactic/anaphylactoid reaction, the subject will be discontinued from the study treatment.

The CTCAE category of “Infusion related reaction” should be used to describe study treatment related infusion reactions, unless the investigator considers another category, such as “Allergic reaction,” “Anaphylaxis,” or “Cytokine release syndrome” more appropriate in a specific situation.

### 6.2.1 Concomitant therapy

In general, concomitant medications and therapies deemed necessary for the supportive care (e.g. such as anti-emetics, anti-diarrhea) and safety of the subject are allowed except when specifically prohibited (see [Section 6.2.2](#)).

The subject must be told to notify the investigational site about any new medications he/she takes after the start of the study treatment. Medications include not only physician prescribed medications, but also all over-the counter medications, herbal medications, food supplements and vitamins.

All medications (excluding the current study treatment), procedures and significant non-drug therapies (including physical therapy and blood transfusions) administered after the subject signs the main study ICF and up to 30 days after the last dose of study drugs must be recorded in the appropriate eCRF.

Each concomitant drug (or supplement) must be individually assessed against all exclusion criteria/prohibited medication. If in doubt, the investigator should contact the Novartis medical monitor before enrolling a subject or allowing a new medication to be started. If the subject is already enrolled, contact Novartis to determine if the subject should continue participation in the study.

## Use of bisphosphonates or RANKL inhibitor

Treatment with bisphosphonates or receptor activator of nuclear factor kappa-B ligand (RANKL) inhibitor for pre-existing bone metastases is permitted, if clinically indicated and at the investigator's discretion following existing local guidelines. Treatment with bisphosphonates or RANKL inhibitor should preferably begin before the study treatment is initiated, but can also be initiated during therapy only if absence of radiological bone disease progression is well documented (in this case, the reason for its use must be clearly documented; i.e. "pre-existing, non-progressing, bone metastases").

## Permitted radiotherapy

Localized radiotherapy for pre-existing, painful bone metastases is permitted. Local bone radiotherapy for analgesic purposes or for lytic lesions at risk of fracture may be carried out if required. If palliative radiotherapy is initiated after start of study treatment, the reason for its use must be clearly documented and progression as per RECIST 1.1 must be ruled out. The study treatment must be interrupted on the days of radiotherapy and can be resumed the day after its completion. Caution is advised for radiation to fields that include lung tissue.

### 6.2.1.1 Permitted concomitant therapy requiring caution and/or action

#### 6.2.1.1.1 Capmatinib

Permitted concomitant therapy requiring caution and/or action when co-administered with Capmatinib are as follows:

- **CYP1A2 substrates with narrow therapeutic index (NTI).**

Capmatinib is a moderate CYP1A2 inhibitor. Co-administration of capmatinib increased sensitive CYP1A2 probe substrate (caffeine) AUC by 134%. CYP1A2 substrates where minimal concentration changes may lead to serious adverse reactions. If co-administration is unavoidable, decrease the CYP1A2 substrates dosage in accordance with the approved prescribing information.

- **Pgp or BCRP substrates.**

Co-administration of capmatinib increased Pgp substrate (digoxin) exposure (AUC and Cmax by 47% and 74%, respectively) and BCRP substrate (rosuvastatin) exposure (AUC and Cmax by 108% and 204%, respectively). Avoid co-administration of capmatinib with P-gp and BCRP substrates where minimal concentration changes may lead to serious adverse reactions. If co-administration is unavoidable, decrease the P-gp or BCRP substrates dosage in accordance with the approved prescribing information

- **Strong CYP3A4 inhibitors.**

Co-administration of capmatinib with a strong CYP3A4 inhibitor (itraconazole) increased capmatinib AUC by 42%. There was no change in capmatinib Cmax. Closely monitor subjects for adverse reactions when using strong CYP3A4 inhibitors concurrently with capmatinib.

- **Moderate CYP3A4 inducers.**

The effect of the moderate CYP3A4 inducer, efavirenz (600 mg once daily for 20 days) coadministered with capmatinib was simulated using the physiologically-based pharmacokinetic (PBPK) models. The models predicted a weak effect of 44% reduction in capmatinib AUC0-12 and 34% reduction in Cmax at steady state compared to administration of capmatinib alone. Caution should be exercised during concomitant use of capmatinib with moderate CYP3A4 inducers. Use an alternative medication with no or minimal potential to induce CYP3A4 during co-administration with capmatinib.

- **Proton Pump Inhibitors (PPIs).**

Co-administration of capmatinib with proton pump inhibitor (rabeprazole) decreased capmatinib AUCinf by 25% and Cmax by 38%. Exercise caution during concomitant use of capmatinib with proton pump inhibitors.

- **Antacid and H2 receptor antagonists.**

As an alternative to proton pump inhibitors, H2-receptor antagonist or antacid can be taken. Capmatinib should be taken at least 3 hours before or 6 hours after an H2-receptor antagonist, and at least 2 hours before or 2 hours after an antacid.

Refer to [Appendix 3](#) for a list of the medications (presented by mechanism of interaction) that require caution when concomitantly used with capmatinib.

### 6.2.1.1.2 Spatalizumab

Hematopoietic colony-stimulating growth factors (e.g. G-CSF, GM-CSF, M-CSF), thrombopoietin mimetics or erythroid stimulating agents are allowed as per local or published guidelines; in case of anemia, thrombocytopenia or neutropenia, potential immune-mediated etiology should be ruled out.

Anticoagulation and anti-aggregation agents are permitted if the subjects are already at stable doses for > 2 weeks at time of first dose of spatalizumab/placebo, and International Normalized Ratio (INR) should be monitored as clinically indicated per investigator's discretion. However, ongoing anticoagulant therapy should be temporarily discontinued to allow tumor sample according to the institutional guidelines.

Subjects with disease metastatic to bone may receive bone-stabilizing agents such as bisphosphonates or monoclonal antibodies intended for this purpose.

### 6.2.2 Prohibited medication

During the course of the study, subjects must not receive other antineoplastic therapies (e.g. investigational drugs, devices, chemotherapy, immunotherapies) or any other therapies that may be active against cancer or that are intended to modulate an immune response. However, limited-field palliative radiotherapy to non-target lesion(s) may be allowed as concomitant therapy upon discussion with the Novartis medical monitor. Such local therapies administered during the study treatment must be entered into the eCRF. The study treatment must be interrupted on the days of radiotherapy and can be resumed the day after its completion.

The use of live vaccines is not allowed during the study and up to 150 days from last dose of spatalizumab or 30 days from the last dose of capmatinib, whichever is longer.

There are no prohibited therapies during the post-treatment follow-up period.

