### Overview of study visit flow (Part 1 and Part 2)

For all subjects tumor molecular pre-requisites will be assessed during screening. EGFR and ALK status will be verified based on tests performed locally as part of standard clinical practice, while MET mutation status will be assessed at a Novartis-designated central laboratory during molecular pre-screening, unless previously determined locally (only local assays agreed by Novartis will be accepted). Additional information regarding the molecular pre-screening and the main screening are provided respectively in [Section 8.1.1](#) and [Section 8.1.2](#).

Subjects with NSCLC of pure squamous cell histology do not need to be tested for an EGFR mutation or ALK rearrangement, however, subjects with pure squamous cell histology already known to have EGFR mutations in exons 19 and 21 or ALK-positive rearrangement will be excluded. Once all eligibility criteria are confirmed, subjects will receive capmatinib 400 mg BID in combination with spartalizumab 400 mg or placebo Q4W in a 28-day cycle.

Subjects will be treated until they experience unacceptable toxicity, disease progression per RECIST 1.1 as determined by investigator assessment (with or without confirmation by BIRC), and/or treatment is discontinued at the discretion of the investigator or the subject. A complete list of the circumstances requiring study treatment discontinuation is provided in [Section 9](#).

Study treatment may be continued beyond disease progression per RECIST 1.1 if, in the judgment of the investigator, there is evidence of clinical benefit, and the subject wishes to continue on the study treatment (for additional details please refer to [Section 6.1.4](#)).

After study treatment discontinuation, an end of treatment visit will be performed, all subjects will then enter the safety follow-up period, which will last for 150 days after last dose of spartalizumab or 30 days after last dose of capmatinib, whichever is longer. For subjects who are transferred to another clinical study or alternative treatment option to continue capmatinib treatment at end of study, no further collection of safety data will be required as part of this study (for details please refer to [Section 9.2.1](#)).

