Color photographs (with metric ruler)				X (If positive at baseline, follow the same schedule as CT/MRI of chest, abdomen, and pelvis. Or if clinically indicated.)						
Electrocardiogram (12-Lead ECG)		X			X					
Blood sample for Capmatinib Extensive and non-Extensive PK sampling		X	X							
IRT Registration/ Treatment Dispensing/ Discontinuation				X (study treatment dispensing only)	X					

Period	Treatment					Post treatment follow-up*				
						Safety Follow-up				
	Visit Name	C3	C4	Subsequent cycles	EOT	30 day	60 day	90 day	120 day	150 day
Days	D1	D1	D1			-	-	-	-	-
Capmatinib administration	X (continuous BID dosing)									
Safety follow-up						X	X	X	X	X

 
• X = assessment to be recorded in the clinical database or received electronically from a vendor; S = assessment to be recorded in the source documentation only.
 
										
*Following the approval of protocol amendment 01, tumor assessment follow-up and survival follow-up will not be performed										

Table 8-2 Assessment Schedule - Part 2 (Randomized part) - obsolete since Part 2 will not be initiated

Period	Screening		Treatment							Post treatment follow-up										
	Visit Name	Molecular assays	Main screening	C1		C2	C3	C4	C5	C6	Subsequent cycles	EOT	Safety Follow-up					Survival Follow-up		
				30 day	60 day	90 day	120 day	150 day												
Days		-28 to -1	D1	D15	D1	D1	D1	D1	D1	D1			-	-	-	-	every 12 weeks			
Informed consent for molecular pre-screening	X																			
Confirmation of EGFR wt and ALK rearrangement negative status (local data)	X																			
Collection of archival tumor sample or newly obtained tumor sample for central MET testing (if no local data available)	X																			
Informed consent		X																		
MET mutation status (result of central testing or local data, if available)	X																			

Final

Period	Screening		Treatment								Post treatment follow-up					
	Visit Name	Molecular assay	Main screening	C1		C2	C3	C4	C5	C6	Subseque nt cycles	EOT	Safety Follow-up			
				30 day	60 day	90 day	120 day	150 day								
Days		-28 to -1		D1	D15	D1	D1	D1	D1	D1			-	-	-	-
Inclusion / Exclusion criteria		X														
Demography		X														
Smoking history		X														
Diagnosis and extent of cancer		X														
Prior antineoplastic therapy (meds, surgery, radiation)		X														
Relevant medical history/current medical conditions		X														

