### **9.2.2 Post treatment follow-up**

After treatment discontinuation, all subjects will be followed for safety, as described in [Section 9.2.2.1](#).

Note: For subjects who transfer to another clinical study or an alternative treatment option to continue provision of study treatment, the follow-up for safety, tumor assessment and survival will not be performed.

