#### **9.2.2.1 Safety follow-up**

All subjects must have safety evaluations for 150 days after the last dose of spartalizumab/placebo and 30 days after the last dose of capmatinib, whichever is longer. The subject will be followed via telephone call or onsite visit (if patient happens to be visiting the site) for the 30-, 60-, 90-, 120- and 150-day follow-up visits. Concomitant medications will be collected until the 30-day safety follow-up has been completed or the start of a new anti-neoplastic therapy, whichever occurs first.

For female subjects of child bearing potential, pregnancy tests will be performed as outlined in [Section 8.4.7](#).

The assessments required during safety follow-up are specified in [Table 8-1b](#) or [Table 8-2](#).

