#### **9.2.2.2 Survival follow up**

Following the approval of protocol amendment 01, survival follow up will not be performed.

After completion of the safety follow-up, subjects will enter the survival follow-up period. Subjects will be contacted by telephone every 12 weeks to follow-up on their survival status. Any new anti-neoplastic therapies that have been started since the last contact date will also be collected during these phone calls. Date of progression on new antineoplastic therapies will also be collected.

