2. its relationship to the study treatment. If the event is due to lack of efficacy or progression of underlying illness (i.e. progression of the study indication) the assessment of causality will usually be 'Not suspected.' The rationale for this guidance is that the symptoms of a lack of efficacy or progression of underlying illness are not caused by the trial drug, they happen in spite of its administration and/or both lack of efficacy and progression of underlying disease can only be evaluated meaningfully by an analysis of cohorts, not on a single subject
3. its duration (start and end dates) or if the event is ongoing, an outcome of not recovered/not resolved must be reported
4. whether it constitutes a SAE (see [Section 10.1.2](#) for definition of SAE) and which seriousness criteria have been met
5. action taken regarding with study treatment. All adverse events must be treated appropriately. Treatment may include one or more of the following:
  - Dose not changed
  - Dose Reduced/increased
  - Drug interrupted/withdrawn
6. its outcome

If the event worsens the event should be reported a second time on the eCRF noting the start date when the event worsens in toxicity. For grade 3 and 4 adverse events only, if improvement to a lower grade is determined a new entry for this event should be reported on the eCRF noting the start date when the event improved from having been grade 3 or grade 4.

Conditions that were already present at the time of informed consent should be recorded in medical history of the subject.

Adverse events (including lab abnormalities that constitute AEs) should be described using a diagnosis whenever possible, rather than individual underlying signs and symptoms.

Adverse event monitoring should be continued for at least 30 days after the last dose of capmatinib or 150 days after the last dose of spartalizumab/placebo, whichever is longer. If a patient starts a post treatment anti-neoplastic therapy sooner than the 30/150 days mentioned above, then only adverse events suspected to be related to study treatment should be collected.

Once an adverse event is detected, it must be followed until its resolution or until it is judged to be permanent (e.g. continuing at the end of the study), and assessment must be made at each visit (or more frequently, if necessary) of any changes in severity, the suspected relationship to the interventions required to treat it, and the outcome.

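### Protocol Section 6.2.2 bans live vaccines for a fixed time after the last dose, then states without exception that nothing is prohibited in that same period (minor wording fix)

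*Protocol*

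**What the plan says.** Protocol Section 6.2.2 first bars other anticancer treatment and anything meant to modulate immunity while the study runs, with a carve-out for limited palliative radiotherapy. It then turns to vaccines: "The use of live vaccines is not allowed during the study and up to 150 days from last dose of" spartalizumab, or 30 days from the last capmatinib dose, whichever is longer. The section closes with "There are no prohibited therapies during the post-treatment follow-up period".

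The length of follow-up is set elsewhere. Section 3, in the overview of visit flow, describes a safety follow-up "which will last for 150 days after last dose of spartalizumab or 30 days after last dose of capmatinib, whichever is longer". Section 9.2.2.1 repeats it: "All subjects must have safety evaluations for 150 days after the last dose of spartalizumab/placebo", with the 30-day capmatinib limit alongside.

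On what post-treatment follow-up now contains, Section 9.2.2 says "After treatment discontinuation, all subjects will be followed for safety, as described in" Section 9.2.2.1. The footnote to Table 8-1b says "tumor assessment follow-up and survival follow-up will not be performed", and Section 9.2.2.2 confirms: "Following the approval of protocol amendment 01, survival follow up will not be performed".

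**The concern.** Two adjacent sentences under the heading for prohibited medication give opposite instructions for the same weeks. One forbids live vaccines after treatment up to a stated limit; the other says that nothing is forbidden after treatment. A site that consults the section about a subject in follow-up, and takes the last sentence at face value, would conclude that a live vaccine is allowed.

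What is at stake is a patient-safety instruction, not an analysis. The amendment 01 rationale says that the vaccine language was revised to make the position on live vaccines clear, and the closing sentence works against that aim.

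**Working it through.** The plan states no figure on this point, so the check compares the time windows and then bounds how many subjects could be affected.

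**1. Do the windows overlap?**

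- End of the live-vaccine ban (Section 6.2.2): the later of last spartalizumab + 150 days and last capmatinib + 30 days.
- End of safety follow-up (Sections 3 and 9.2.2.1): the later of last spartalizumab + 150 days and last capmatinib + 30 days.
- Other post-treatment phases: none. Tumor-assessment and survival follow-up were removed (Table 8-1b footnote, Section 9.2.2.2).

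The two end points are identical. The closing sentence cannot refer to a later phase that begins after the ban has expired, because no such phase remains. The post-treatment part of the ban therefore coincides with the whole follow-up period.

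**2. Who could be affected?**

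Inputs: 31 subjects treated (Section 4.1); 19 still on capmatinib on 06-Sep-2021, enrollment halted on 28-Jul-2021 with spartalizumab stopped, and 3 subjects in screening who started on capmatinib alone (Amendment 1, Study Update and rationale); amendment dated 13-Oct-2021. I assume that no spartalizumab was given after 28-Jul-2021.

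- Off treatment by 06-Sep-2021: 31 − 19 = 12 at most.
- Capmatinib limit for those 12: 06-Sep-2021 + 30 days = 06-Oct-2021 at the latest. That is 7 days before the amendment date, so this limit had already passed.
- Spartalizumab limit, upper bound: 28-Jul-2021 + 150 days = 25-Dec-2021, and 25-Dec-2021 − 13-Oct-2021 = 73 days.
- Spartalizumab limit, lower bound: 13-Oct-2021 − 150 days = 16-May-2021. A last spartalizumab dose on or before that date leaves 0 days.
- Later discontinuations: 0 to 19; the documents do not give the number.

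**3. Which limit governs for the later discontinuations?**

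On the same assumption the 150-day limit closes for everyone by 25-Dec-2021. The 30-day capmatinib limit becomes the later of the two for anyone whose last capmatinib dose falls after 25-Dec-2021 − 30 days = 25-Nov-2021, and for an earlier last dose if spartalizumab stopped before 28-Jul-2021. From then on the window is 30 days. For the three subjects who started on capmatinib alone, only the 30-day limit ever applies.

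Subjects who transfer to another source of capmatinib have no safety follow-up in this study (Section 9.2.2) and are not affected.

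**4. Do other sections settle it?**

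- Section 6.2.2.2 repeats the ban, but only the 150-day spartalizumab part. The 30-day capmatinib limit for live vaccines appears only in Section 6.2.2, next to the sentence that appears to cancel it.
- Section 6.2.1 asks sites to check each concomitant drug against the prohibited list and to contact the medical monitor if in doubt. For follow-up, that check leads back to the closing sentence of Section 6.2.2.

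**The case against.** The strongest reply is that the section explains itself. The opening paragraph bars anticancer and immune-modulating therapies without a clear end date. The closing sentence uses the same noun, therapies, and supplies that end. The vaccine sentence carries its own dated limit and needs no closing rule. Read literally, the closing sentence would leave the post-dose limits one line above without effect, and readers normally let a specific dated rule override a general one.

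Other sections support this reading. Section 10.1.1 plans for new anticancer treatment inside the window ("If a patient starts a post treatment anti-neoplastic therapy sooner than the 30/150 days mentioned above"), and Section 10.1.3 and Table 8-1b do likewise. Nothing in the protocol contemplates live vaccination then. Section 6.2.2.2 restates the 150-day ban after the disputed sentence, with no exception for follow-up.

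Most of this stands as an account of what was meant, and it is why the practical risk is small. It does not remove the conflict. The limitation to anticancer and immune-modulating treatment is not written, the unqualified sentence directly follows the vaccine ban, and the restatement in Section 6.2.2.2 does not cover the capmatinib limit. The objection is also right that the exposure is bounded: 73 days is a ceiling that shrinks with each day before local approval of the amendment, and the documents give no figure for live-vaccine use or harm.

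**Conclusion.** The closing sentence of Section 6.2.2 is wrong as written, at the lowest severity. Read literally, it permits throughout post-treatment follow-up what the preceding sentence forbids for the same period.

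The exposure is at most 12 subjects off treatment by 06-Sep-2021, with 0 to 73 days of the ban remaining at the amendment date, plus 0 to 19 later discontinuations. These bounds rest on there being no spartalizumab dose after 28-Jul-2021 and on the subject counts in the protocol. The dated ban would probably be followed in practice. No endpoint, analysis set, safety summary or sample-size figure changes.

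**What to change.** Begin the last sentence of Section 6.2.2 with an exception clause, for example: *Except for live vaccines, as stated above,* and leave the rest of the sentence as it is. This keeps the likely intent, adds no new restriction and removes the contradiction for both the spartalizumab and the capmatinib limits.

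The cost is one clause at the next amendment, or one clarifying line in a site letter. It does not warrant an amendment of its own.
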